### **Aim 2**

There is one primary outcome for Aim 2: the association between practice and concordance at Visit 2. Concordance is binary and equals 1 when both participant and clinician identify an abnormality or agree on its absence; thus, the statistical analysis is premised on detecting an anal abnormality, not a cancer. We postulate that practicing the ASE or ACE between visits will be associated with ASE/ACE and DARE concordance at Visit 2. To derive unbiased estimates in multivariable modeling for the association between practice and concordance, we will use directed acyclic graphs to identify potential confounders to include in models (e.g., age, ethnicity, race, city, anxiety, chronic disease, and, for ACE, co-teaching and reported familiarity with a companion’s body) and intermediate variables to exclude from multivariate modeling; however, given successful randomization, bias, including confounding, should be minimized. Both intent-to-treat and per-protocol analyses will be conducted (we expect a similar proportion of persons in the practice and non-practice arms to switch arms of their own accord, i.e., crossover, between visits). The association will be assessed with logistic regression. After univariate analyses, variables where  $p \leq 0.25$ , and which are not intermediate variables, will be added to a multivariable model using backward selection with binary practice (yes/no) retained in the model. After adjustment for potential confounders, factors where  $p < 0.05$  (two-sided) will be considered statistically significant. Adjusted and un-adjusted odds ratios will be reported with 95% confidence intervals. We will use a similar approach to derive unbiased estimates in multivariable modeling for the association between continuous waist size and concordance; however, we will also use ROC curves to ascertain the potential for a threshold effect of waist circumference size on concordance. We will also assess the full set of other study data and their potential associations with concordance. For multiple comparisons we will use the False Discovery Rate. Finally, we will investigate effect modification by age and individual/couple status.

For the Aim 2 hypothesis, that practice will be associated with concordance in all persons at Visit 2, sample size will be adjusted downward by dropouts and non-resolving abnormalities from Visit 1. We expect 11% of persons ( $n=88$ ) to have an abnormality at Visit 1 (based on pilot data) with most of these being hemorrhoids and condyloma. We conservatively expect 50% of hemorrhoids and condyloma to resolve in 9 months; thus, there will be a minimum of 44 non-resolving events from Visit 1 and another 10% of persons will dropout ( $800-44=756$ ;  $756-76=680$ ). We have 80% power to detect an odds ratio of at least 1.55 or larger if concordance is 85% and  $n=680$ .

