#### **Arm 1 - Practice Arm**

Persons in the practice arm will pick a date three months after Visit 1. The study coordinator will record the date and provide participants written ASE/ACE instructions. Participants who report more than minimal pain associated with ASE/ACE at Visit 1, or otherwise have contraindications based on DARE results, will be asked to not to practice if randomized to the practice Arm. However, all persons will be asked to attend Visit 2 to engage in study activities that are not contraindicated at the time of Visit 2. Participants will be reminded that we will schedule a Visit 2 appointment and that we will also contact them in 3 months and periodically to keep in touch to support study retention.

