#### **Arm 2 – Non-practice Arm**

Persons in the non-practice arm will be reminded that we will schedule a Visit 2 appointment and that we will also contact them periodically to keep in touch to support study retention. Persons in the non-practice arm will be neither encouraged to practice nor discouraged from practice. If asked about practice, study staff will reply that the participant is not expected to practice since the ASE/ACE is not known at this time to be beneficial. The PAC Palpation Study is trying to determine if it’s beneficial.

After end-of-Visit 1 study staff will provide a \$50 incentive and also tell the participants about the Referral Program for recruitment. Anticipated visit duration is about 75 and 90 minutes for individuals and couples, respectively.

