### **Between Visit 1 and Visit 2 study procedures**

#### Arm 1 – Practice.

*If participant had a normal DARE at Visit 1, OR if participant had an abnormal DARE at Visit 1 that required no referral (e.g., a scar or non-prolapsed hemorrhoids),* study staff will make reminder calls (or emails/texts) and follow-up calls for the scheduled practice session. At the follow-up calls, study staff will record the participant's result for the self/companion exam and the level of anxiety and pain, if any, associated with the exam. If the participant reports more than minimal pain and anxiety, they will be asked to return to the clinic for an HCP exam.

If a new abnormality is detected by the participant, i.e., an abnormality not recorded at Visit 1, the study coordinator will request they return to the study clinic site for a clinical examination. While requesting they return to the clinic, staff will record the participant description of the abnormality, and their level of anxiety and pain associated with the ASE/ACE practice. When the participant returns to the clinic, staff will record medical outcomes for each person.

Participants not wanting to return to the clinic will be provided referrals by the health care provider at the clinic. Efforts will be made to contact persons once each week for up to four weeks to encourage a return to the study clinic or completing of the referral elsewhere.

*If participant had an abnormal DARE at Visit 1 that required referral (e.g., condyloma or suspicious lesion),* the person can still participate in practice unless the clinician advises that the ASE/ACE is contraindicated due to the Visit 1 abnormality, or the person reported more than minimal anxiety or pain due to the ASE/ACE at Visit 1. During follow up, staff will ask about referral completion, resolution of the abnormality, and practice ASE/ACE results. If referral has still not been completed, staff will again encourage completion of referral or coming back to an upcoming study clinic for another DARE.

Participant activity and results between Visit 1 and Visit 2 will be documented in REDCap.

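### The undefined Aim 2 per-protocol set does not say how to treat people whom staff ask not to practise in the practice arm only; the usual reading would unbalance the arms

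*Combined protocol and SAP*

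**What the plan says.** The Arm 1 - Practice Arm section identifies a group by Visit 1 status: "Participants who report more than minimal pain associated with ASE/ACE at Visit 1, or otherwise have contraindications based on DARE results". It says that these people "will be asked to not to practice if randomized to the practice Arm". The Arm 2 – Non-practice Arm section has no counterpart: "Persons in the non-practice arm will be neither encouraged to practice nor discouraged from practice".

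The Aim 2 analysis section announces two analyses: "Both intent-to-treat and per-protocol analyses will be conducted (we expect a similar proportion of persons in the practice and non-practice arms to switch arms". The parenthesis in full limits this to voluntary switching: "we expect a similar proportion of persons in the practice and non-practice arms to switch arms of their own accord". The section does not define the per-protocol set, does not say which analysis is primary, and does not mention non-practice on staff instruction. The regression is described as "backward selection with binary practice (yes/no) retained in the model", without saying whether that variable is the assigned arm or what the person did.

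Two other sections bear on the point. Preparation for Visit 2 withholds the Visit 2 self- or companion exam, in either arm, from anyone with a prior contraindication until a clinician clears them. The section on procedures between Visits 1 and 2 describes again who is held back in Arm 1. For people needing referral, it adds anxiety as a ground: "the person reported more than minimal anxiety or pain due to the ASE/ACE at Visit 1". For people with a normal exam, or an abnormality needing no referral, it describes practice reminders and states no exception for Visit 1 pain.

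**The concern.** A per-protocol comparison is fair only if the same kinds of people are kept in both arms. Here a Visit 1 characteristic makes a person a non-practiser by instruction in Arm 1, while the same person in Arm 2 conforms by doing nothing. The plan's reassurance about similar switching covers voluntary crossover. It is silent on this directed non-practice, which can occur in one arm only.

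If flagged people agree with the clinician less often at Visit 2, dropping them from Arm 1 alone raises that arm's concordance with no effect of practice. If the data are analysed by actual practice, they move into the comparison group and the gap widens. Because the plan does not name intent-to-treat as primary, an analysis affected in this way could carry the Aim 2 conclusion.

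**Working it through.** **The plan's own figures.** The Aim 2 count reproduces: 800 − 44 = 756; 10% of 756 is about 76; 756 − 76 = 680. With 1:1 allocation that is 340 per arm. The stated 80% power for an odds ratio (OR) of 1.55 at 85% concordance does not reproduce with 340 per arm: two-sided power is 0.47, 0.52 or 0.59 with 85% as the control, average or practice rate. That is a separate matter and nothing below depends on it.

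**Inputs.**
- Concordance 85% in each arm as randomised, with no practice effect: the rate is the plan's (Aim 2), the absence of effect is the null.
- Flagged share f: not in the documents; assumed 2%, 5% and 10%. The expected 11% with any Visit 1 abnormality is not an estimate of f: it includes abnormalities needing no referral, for which practice goes ahead, and it leaves out pain without an abnormality.
- Visit 2 concordance c in flagged people: not in the documents; assumed 50% to 85%.
- All flagged people are taken to contribute a Visit 2 result, which overstates the effect where a contraindication has not been cleared.

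**Usual per-protocol reading** (practised in Arm 1, did not practise in Arm 2). Flagged people leave Arm 1 only:

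p1 = (0.85 − f·c)/(1 − f); OR = [p1/(1 − p1)] / [0.85/0.15]

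Example, f = 0.10 and c = 0.70: p1 = (0.85 − 0.07)/0.90 = 0.8667. The odds are 0.8667/0.1333 = 6.50 against 0.85/0.15 = 5.667, so OR = 1.147.

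The false-positive rate is for a two-sided 5% test of two proportions, with 340(1 − f) against 340 people. With d = p1 − 0.85, SE0 the pooled and SE1 the unpooled standard error, it is Φ((d − 1.96·SE0)/SE1) + Φ((−d − 1.96·SE0)/SE1).

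| f | c | p1 | OR under no effect | False-positive rate | n |
|---|---|---|---|---|---|
| 2% | 70% | 0.853 | 1.02 | 0.051 | 333 v 340 |
| 5% | 70% | 0.858 | 1.07 | 0.059 | 323 v 340 |
| 10% | 80% | 0.856 | 1.05 | 0.054 | 306 v 340 |
| 10% | 70% | 0.867 | 1.15 | 0.092 | 306 v 340 |
| 10% | 60% | 0.878 | 1.27 | 0.175 | 306 v 340 |
| 10% | 50% | 0.889 | 1.41 | 0.307 | 306 v 340 |
| any | 85% | 0.850 | 1.00 | 0.050 | |

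**Analysis by actual practice.** Flagged people move to the non-practice group, whose rate becomes (0.85 + f·c)/(1 + f). At f = 10% the OR is 1.08, 1.27 and 1.78 for c = 80%, 70% and 50%. Example, c = 0.70: (0.85 + 0.07)/1.10 = 0.8364, odds 5.111, and 6.50/5.111 = 1.27.

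**Flag applied to both arms.** Both rates become (0.85 − f·c)/(1 − f), so the OR is 1.00 for any f and c. The numbers left are 680(1 − f): about 666, 646 and 612 at 2%, 5% and 10%.

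**The case against.** A reader might infer that the plan's expectation of similar switching is contradicted by its own rule. It is not: the sentence concerns people who switch by choice, and following a staff instruction is not that. The sentence is incomplete, not untrue.

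A reader might also infer that the comparison is unbalanced by design. The documents do not go that far, because the set is undefined. Someone who was asked not to practise and complied has followed the protocol. If such people count as adherent and stay in Arm 1, any effect is diluted and no spurious benefit arises. The exclusion is an inference from the usual definition.

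Several provisions shrink the affected group. Uncleared contraindications give no Visit 2 exam in either arm. Unresolved diagnosed condyloma or hemorrhoids are excluded at entry. A fissure, fistula or other contraindication to the clinician exam ends Visit 1 before randomisation. The sample-size count also subtracts 44 non-resolving abnormalities, though the analysis text states no such exclusion. What remains is mainly people with pain only and people whose contraindication is later cleared. For pain with a normal exam, the two Arm 1 descriptions differ on whether they are held back at all.

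Nor is the direction established. The plan expects ASE sensitivity of at least 70% and specificity of at least 90%, which makes lower agreement plausible where an abnormality persists. But participants learn their Visit 1 result and may report a known abnormality correctly later. For pain alone the documents give no concordance figure.

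Covariate adjustment would help only if Visit 1 pain and contraindication were in the model. They are not among the example confounders, and selection by p-value could drop them.

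These points limit the size and certainty of the bias. They do not supply a definition of the set, or a rule that treats the same Visit 1 status alike in both arms.

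**Conclusion.** The point holds in a limited form. The instruction not to practise applies to one arm only, the per-protocol set is undefined, and the stated reassurance does not cover this kind of non-practice. Under the usual definition, or an analysis by actual practice, flagged people would be removed from or moved out of one arm only.

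Whether this matters depends on two quantities that the documents do not give. At 70% concordance in flagged people it is negligible with 2% flagged (OR about 1.02), small at 5% (1.07) and noticeable at 10% (1.15). At 10% flagged it ranges from 1.05 to 1.41 as their concordance falls from 80% to 50%, against a design OR of 1.55. It vanishes if their concordance equals that of the rest. These are unadjusted figures under assumed inputs. A spurious benefit is therefore a possibility to be closed off, not a demonstrated result. The intent-to-treat comparison is not affected by this mechanism.

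**What to change.** 1. Record pain and contraindication status at Visit 1 for every participant before the allocation is generated, or at the latest before it is disclosed. The clinician's result already exists when the coordinator randomises. When pain is recorded is not stated: it is not among the listed post-exam questions, and randomisation takes place during that questionnaire. A small added recording step may be needed.
2. Define the per-protocol set, and exclude flagged people from both arms on that Visit 1 record.
3. Name intent-to-treat as the primary Aim 2 analysis, and state whether the practice variable in the model is the assigned arm or actual practice.
4. Qualify the sentence on similar switching to say that it does not cover non-practice directed by staff.
5. Reconcile the two Arm 1 descriptions of who is held back from practice, so that the flag has one meaning. Which clinical rule applies is for the study team to decide.

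The cost is one recorded flag, a few sentences, and a somewhat smaller per-protocol control group: about 7, 17 or 34 of 340 controls at 2%, 5% or 10% flagged.

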The first 40 persons in each city will receive a second DARE done by another experienced clinician immediately after the first DARE done by the primary clinician. The clinicians will be kept separate for the two DAREs and not disclose their findings to each other. The second DARE is done to assess the reliability and repeatability of the primary clinician’s DARE.

Once the clinician leaves the exam room, participants will remain and conduct the ASE/ACE. Participants will be trained to stop the procedure if pain is felt. The participant will record on a form the ASE/ACE result: either normal or abnormal. The participant will inform staff that the ASE/ACE is complete. If the participant detects an abnormality, staff will ask if the abnormality was at the perianus and/or anal canal, what it felt like, (i.e., hard or soft) and its size (using varying sizes of circles on paper). Persons will then complete a Post-Exam CASI in the exam room (one member of a couple will do the CASI in another room to give each participant privacy). The couples’ protocol mirrors the individuals’ protocol except that each partner will ask the other for consent before performing the ACE. Prostate and distal rectal palpation will neither be taught nor expected.

The Visit 1 post-exam CASI requires ~20 minutes to complete and asks about ASE/ACE acceptability and self-efficacy, in addition to intentions-to-seek subsequent care, body positioning for the exam, history of anal self-exams, alcohol use, recent sexual behavior (type and frequency), and anogenital hygiene. Questions to support cost effectiveness analysis are included.

While the participant completes the post-exam CASI, the study coordinator will use REDCap to randomize the participant (Arm 1 – practice or Arm 2 – control); if the person is a true negative (the coordinator will possess both participant and clinician results at this point) the study coordinator will check REDCap to determine if this true negative will receive a qualitative interview.

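### Aim 2 names only ordinary logistic regression, with no method for correlation within ACE couples; it also leaves the primary estimate of the practice effect unranked

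*Combined protocol and SAP*

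**What the plan says.** The Aim 2 part of the Statistical Analysis section sets one primary question, whether practice is associated with concordance at Visit 2. On the model it says "The association will be assessed with logistic regression". It describes two routes to covariates. One uses directed acyclic graphs (DAGs) to pick confounders and gives examples that include city and some specific to couples ("for ACE, co-teaching and reported familiarity with a" companion's body). The other takes variables with univariate p of 0.25 or less, "and which are not intermediate variables, will be added to a multivariable model using backward selection with binary practice (yes/no) retained in the model".

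On what is reported, it says "Both intent-to-treat and per-protocol analyses will be conducted" and "Adjusted and un-adjusted odds ratios will be reported with 95% confidence intervals". Statistical significance is judged at two-sided p < 0.05 after adjustment for confounders, and False Discovery Rate control covers multiple comparisons. It closes with "Finally, we will investigate effect modification by age and individual/couple status".

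Visit 1 Detail says that "the study coordinator will use REDCap to randomize the participant" and, of the Visit 1 findings, that "the coordinator will possess both participant and clinician results at this point". The Randomization section allocates half of the participants in each city to practice. Neither section says whether the two members of a couple are allocated together. Visit 2 Study Procedures says that switches from ACE to ASE will be accounted for in the analyses; that concerns change of exam type, not correlation between partners.

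**The concern.** Partners attend the same visit and each examines the other, so their concordance outcomes may well be correlated. Ordinary logistic regression then gives standard errors that are too small for any term that partners share. Aim 2 plans such terms: ASE/ACE status, couple-specific factors, and the individual/couple interaction with practice. If partners share an arm, practice itself is such a term.

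The second, supporting matter is that the trial's only randomised comparison can be reported as several odds ratios. Intention-to-treat is not ranked against per-protocol, and the two covariate routes are not reconciled. Which result carries the Aim 2 hypothesis could therefore be decided after the data are seen.

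**Working it through.** **The plan's own figures.** The documents give no figure for within-couple correlation, so there is none to reproduce. The Aim 2 sample size follows as stated: 800 − 44 = 756, and 756 − 76 = 680. The stated 80% power for an odds ratio of 1.55 at 85% concordance does not reproduce with 680 in total at two-sided 5% (about 47 to 59%, depending on which rate the 85% is). That is a separate matter, and nothing below uses it.

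**Inputs.** 600 individuals and 200 in couples (Aim 1), which add to the 800 in Sample Size only if the 200 counts people. ICC of 0.1 to 0.3 is an assumption.

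**Formula.** With a design effect DE, a nominal two-sided 5% test has true type I error 2 × [1 − Φ(1.96/√DE)].

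- Overall test of arm, partners in the same arm: a quarter of people are in pairs, so DE = 1 + 0.25 × ICC.
- Arm within ACE (same arm), or any ACE factor identical in both partners: DE = 1 + ICC.
- ASE/ACE status, or the individual/couple interaction with arm (same arm): the variance is proportional to 1/600 + (1 + ICC)/200. Divided by 1/600 + 1/200, this gives DE = 1 + 0.75 × ICC.

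| Test | DE at ICC 0.1, 0.3 | Type I error | Depends on allocation of partners? |
|---|---|---|---|
| ASE/ACE status | 1.075, 1.225 | 5.9%, 7.7% | No |
| ACE factor shared by partners | 1.10, 1.30 | 6.2%, 8.6% | No |
| Arm, overall | 1.025, 1.075 | 5.3%, 5.9% | Only if same arm |
| Arm within ACE | 1.10, 1.30 | 6.2%, 8.6% | Only if same arm |
| Individual/couple interaction | 1.075, 1.225 | 5.9%, 7.7% | Only if same arm |

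**Simulation check.** n = 680 (510 ASE, 85 couples), 85% concordance, beta-binomial pairs, 20,000 trials per setting, ICC 0.1, 0.2, 0.3.

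- Same arm, ordinary logistic regression: overall 5.1, 5.4, 5.7%; within ACE 5.9, 7.0, 8.2%; interaction 5.5, 6.6, 7.3%.
- Partners randomised individually: these three stay at 4.8 to 5.1%.
- Either scheme: ASE/ACE status 5.5 to 7.4%, shared ACE factor 5.9 to 8.3%.
- Couple-clustered standard errors: 4.6 to 5.5% throughout.

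**Other reading of the couples figure.** If 200 couples means 400 of 1,000 people, the overall DE is 1 + 0.4 × ICC, giving 5.5 to 6.4%. For status and interaction it is 1 + 0.6 × ICC, giving 5.7 to 7.1%.

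**Why the estimate should be named.** Take 85% in controls and an odds ratio of 1.55, so 0.8978 with practice. Assume a fraction x switches in each arm. The assigned-arm rates are 0.85 + 0.0478x and 0.8978 − 0.0478x. At x = 10% these are 0.8548 and 0.8930, odds ratio 1.42; at x = 20% they are 0.8596 and 0.8882, odds ratio 1.30. By actual practice the figure stays at 1.55. This is ordinary dilution, not bias, but the two analyses answer different questions.

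**The analysis set.** The Aim 2 sample-size paragraph subtracts 44 people whose Visit 1 abnormalities do not resolve. Resolution is known only after randomisation, and the plan does not say whether these people are left out of the analysis or only of the power calculation.

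**The case against.** The strongest reply is that the primary question is barely touched. The randomisation text speaks of the participant, and if partners are allocated one by one the test of arm stays near 5%. Even with partners in the same arm, the simulated overall rate of 5.1 to 5.7% overlaps the 4.6 to 5.5% seen with clustered errors. That stands. A reader might infer that the trial's main comparison is materially anti-conservative; the documents do not support this, since they neither put partners in one arm nor give an ICC.

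The larger figures belong to secondary tests, and the top of the range needs a factor identical in both partners. Familiarity with a companion's body is reported by each person and need not be. If the factor's own within-couple correlation is r, DE = 1 + r × ICC; at an assumed r = 0.5 this is 1.05 to 1.15, or 5.6 to 6.8%. ASE/ACE status, however, is shared by definition unless a couple separates. False Discovery Rate control does not help, because it takes the p-values as valid.

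The gap in ranking is also narrower than it may look. Significance is tied to the adjusted model, which leans away from the unadjusted odds ratio. The arms are labelled practice and no practice, so the retained practice term reads naturally as assigned arm. Both analysis sets are promised.

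Two stronger readings should be set aside. A reader might infer that backward selection will remove city or distort the practice effect. But the DAG route lists city among the confounders to include, and in simulation selected versus fixed covariates moved the practice odds ratio by a median of only 0.8%. A reader might also infer that per-protocol exclusions would fall on the practice arm alone, because only that arm is asked not to practise after pain or a contraindication. Per-protocol is not defined, and Preparation for Visit 2 withholds the Visit 2 exam from uncleared people with a prior contraindication in either arm, so no such imbalance can be shown.

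**Conclusion.** The concern holds for the couples. As written, Aim 2 tests of ASE/ACE status and of factors shared by partners use standard errors that are too small. True error is about 5.9 to 7.7% and 6.2 to 8.6% at nominal 5%, however partners are randomised. The test of arm overall, arm within ACE and the individual/couple interaction are affected only if partners share an arm, which the plan leaves open. The sizes rest on an assumed ICC of 0.1 to 0.3 and on 200 of 800 people being in couples. They are modest, and the correction is nearly free.

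The unranked intention-to-treat and per-protocol analyses and the two unreconciled covariate routes are mainly missing detail. They would not carry the point alone, but are worth settling in the same edit. No power gain and no material change in the odds ratio is claimed for fixed covariates. This is a change that should be made, held with medium confidence.

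**What to change.** 1. Use couple-clustered standard errors (robust or GEE) in every Aim 2 model that includes ACE pairs, and carry a couple identifier in the dataset.
2. State whether partners are randomised together or individually.
3. Name as primary the intention-to-treat logistic model of Visit 2 concordance by assigned arm, with three fixed covariates: city, ASE/ACE status at Visit 1, and Visit 1 concordance as held at randomisation, before any adjudicating DARE.
4. Do not adjust the primary model for practice done after randomisation. Preparation for Visit 2 collects this from control participants to handle confounding; keep it for secondary analyses.
5. State how the primary analysis treats people with non-resolving Visit 1 abnormalities.
6. Keep the screening and backward-selection models for the exploratory search for factors, and say how they relate to the DAG-chosen confounders.

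The cost is SAP wording, one identifier (the text shown mentions none) and a few degrees of freedom. Intervals become slightly wider: the simulated standard error of the log odds ratio was 0.24 unadjusted and 0.24 to 0.27 with fixed covariates, so at most about 12% (0.27/0.24 = 1.125).

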### **Randomization**

At the end of Visit 1, all participants will be randomized to one of two conditions: Arm 1 (practice) or Arm 2 (no practice). One-half of participants in each city will be randomly selected and encouraged to practice the ASE/ACE 3 months before Visit 2. Persons randomized to the control arm will neither be encouraged nor discouraged from practicing the ASE/ACE.

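### Aim 2 looks for a waist-size threshold with ROC curves, which give a best cut-point whether or not a threshold exists

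*Combined protocol and SAP*

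**What the plan says.** The Statistical Analysis section, Aim 2, sets one primary question: "There is one primary outcome for Aim 2: the association between practice and concordance at Visit 2". The outcome is defined so: "Concordance is binary and equals 1 when both participant and clinician identify an abnormality or agree on its absence".

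Waist is a further factor with its own sentence. That sentence starts with a continuous analysis: "We will use a similar approach to derive unbiased estimates in multivariable modeling for the association between continuous waist size and concordance". It then adds a second tool: "we will also use ROC curves to ascertain the potential for a threshold effect of waist circumference size on concordance". Multiplicity is handled in general terms: "For multiple comparisons we will use the False Discovery Rate".

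The plan gives no cut-point rule, no test of non-linearity, no change-point model, no validation or interval for a cut-off, and no allowance for searching over cut-offs. It does not say which visit's waist or concordance is used, although waist is measured at both visits (Visit 1 Detail; Visit 2 Study Procedures). ROC curves are the only tool named for the threshold question.

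**The concern.** The question is about shape: does concordance stay level up to some waist size and then drop? The usual outputs of an ROC analysis, the area and the best cut-point, describe how well waist ranks discordant above concordant results. They do not distinguish a drop at one point from a steady decline, and a best cut-point exists even when waist is irrelevant.

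The second problem is selection. If the groups on either side of a data-chosen cut are compared as though the cut had been fixed in advance, the p-value is too small and the odds ratio too large. False Discovery Rate control works on the p-values handed to it. The search over cut-points sits inside one of those p-values, so it goes uncorrected.

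At stake is how the waist result is described. A gradual decline, or chance, could be presented as a waist size above which the self- or companion exam agrees less well with the clinician.

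**Working it through.** **Inputs from the documents.** The plan states no figure for the waist analysis. The Aim 2 sample size reproduces: 800 × 0.11 = 88 abnormal at Visit 1; half not resolving = 44; 800 − 44 = 756; 10% dropout ≈ 76; 756 − 76 = 680. The 80% power statement attached to that n concerns practice. A two-proportion calculation with 340 per arm does not reproduce it (0.47 to 0.59 two-sided at odds ratio 1.55), but nothing here depends on it. Discordance is taken as 15% (85% concordance in the Aim 2 power statement) and 7% (93% pilot concordance in Background). That is about 680 × 0.15 = 102 and 680 × 0.07 ≈ 48 discordant results.

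**Assumptions not in the documents.** Waist is normal with mean 95 cm and SD 14 cm. The cut-point is the one with the largest Youden index. The two groups are compared by an uncorrected chi-square test.

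**Formulas.**
- Youden index at cut c: J(c) = Pr(waist > c | discordant) − Pr(waist > c | concordant). The chosen cut maximises |J| (direction free) or J (larger waist worse).
- Test at the cut: z = (p1 − p2) / √[p(1 − p)(1/m1 + 1/m2)], significant if |z| > 1.96. Here p1, p2 and m1, m2 are the discordance rates and sizes of the two groups, and p is the overall rate.
- Non-linearity: LR = 2(log-likelihood with spline − log-likelihood with linear waist), referred to chi-square on (knots − 2) degrees of freedom.

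**Does the best cut identify a step?** Median best J in simulation:

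| True relation | Median best J |
|---|---|
| Linear, odds ratio 1.4 per SD, no threshold | 0.18–0.20 |
| True step, odds ratio 2.5 above +0.8 SD | 0.19–0.21 |

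The two ranges overlap, so the index does not separate the shapes.

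**How often is the chosen cut significant?** (n=680, 7% and 15% discordance)

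| True relation | p<0.05 at the best cut |
|---|---|
| No effect, direction free | 41–43% |
| No effect, larger-is-worse only | about 25% |
| Linear, odds ratio 1.4 per SD, no threshold | 89–97% |

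With no effect, the median one-directional odds ratio at the chosen cut is about 1.7 (7% discordance) or 1.5 (15%), although the truth is 1.0. With the linear effect, the 5th–95th percentile range of the cut is about 86–109 cm (7%) or 87–107 cm (15%).

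**Dependence on settings.** With waist recorded to the nearest 0.5 cm and SD 13 cm, the no-effect rate is about 37% at n=680. It is 38.5% at n=800 with 93% concordance, which would apply if Visit 1 were used.

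**Would correcting for the search be enough?** At 15% discordance, allowing for the search raises the critical value from 1.96 to about 2.97 and brings the no-effect rate to 5.8%. But 68% of gradual effects (odds ratio 1.35 per SD) are still flagged, because such a test detects association, not a step.

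**Does a direct test of shape do better?** A four-knot spline likelihood-ratio test at 15% discordance gave false signals in 4.2% of trials with no effect and 5.4% with a gradual effect of odds ratio 1.35 per SD. Runs across settings gave 3–7%. Its power for the step above was about 12–28%.

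**The case against.** Several points on the other side stand.

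- The plan names no Youden rule, no dichotomisation, no test on either side of a cut and no commitment to report one. The simulated procedure is an assumption about how the ROC curve would be used. A reader might infer that a spurious cut-off is likely to be reported; the text does not support that, and with no waist effect a naively significant cut appears in a minority of trials.
- The 89–97% is not a rate of false associations. Waist does matter in that scenario, so a difference across a cut is a true finding. Only its reading as a step would be wrong.
- Waist is also modelled as continuous, with odds ratios and 95% confidence intervals, so that estimate would stand beside any ROC result. If a cut were examined only after continuous waist reached p<0.05, the no-effect error could not exceed about 5%. The plan does not state that condition, and it would not help when the effect is real but gradual.
- A reader might infer that a cut-off would steer people with larger waists away from self-examination. Nothing in the documents says so, and waist is in no aim or hypothesis.
- The remedy is imperfect: a test of non-linearity responds to any curvature and has low power for a step.
- The full ROC curve is not empty of information about shape: a pure step would give straight segments meeting at a corner. But the plan names no test of that feature, and judging it by eye from roughly 48 to 102 discordant results is not a test.

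None of this makes the ROC analysis an answer to the threshold question. Its near-certain significance when a step exists (99% in one set of runs) is nearly matched when there is only a slope.

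**Conclusion.** The point holds as a mismatch between question and method: ROC curves are the only tool named for the threshold question, and they give a best cut-point whatever the shape. If the best cut were tested without correction, the error with no waist effect would be about 41–43%, or about 25% in one direction, against a nominal 5%. A gradual effect of odds ratio 1.4 per SD would produce a significant cut in 89–97% of trials.

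These sizes rest on n=680, 7–15% discordance, the assumed waist distribution and effect, the Youden rule and an uncorrected test. A misleading waist cut-off is a risk and not a likely outcome of the plan as written. The analysis is secondary, and the primary Aim 2 comparison of practice and concordance is unaffected. The change is still worth making, because it is cheap and addresses the question the plan asks.

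**What to change.** In the waist sentence of Aim 2, replace the ROC threshold search with:

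1. waist as a restricted cubic spline with 3–4 pre-set knots in the same logistic model;
2. a likelihood-ratio test of non-linearity against linear waist;
3. a plot of estimated concordance against waist with its confidence band.

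Label any cut-off exploratory, and report it with a bootstrap interval and an optimism-corrected odds ratio. State in the same edit which visit's waist and concordance are used.

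Cost: a short change to the text, slightly more code, 1–2 extra degrees of freedom and no new data. The real downside is low power for a true step, about 12–28% for an assumed odds ratio of 2.5 above +0.8 SD. The plan should therefore say that a non-significant test does not show that there is no threshold, and that the fitted curve and its band carry the interpretation.
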